5.5.1 Reasons for Termination, Discontinuation or Disqualified

At a study subject last visit (scheduled or unscheduled), they will have their masked punctal plug removed and a study exit case report form (CRF) must be completed, whether or not the study subject completed the final study visit (Visit 7, day 14 post-op). The reason for any early exiting from the study will be indicated on the study exit form and all efforts will be made to complete and report the observations as thoroughly as possible. The primary reason for a study subject early exiting the study should be selected from the following standard categories (see Sections 5.5.1.1 – 5.5.1.3 below).

5.5.1.1 Reason for Termination

A study subject will be terminated from the study if in the Investigators medical judgment, it was in the best interest of the study subject that developed or reported: a) moderate to severe signs or symptoms of ocular inflammation or pain, b) reported a serious AEs, regardless of relation to the study drug/device or has died.

5.5.1.2 Reason for Discontinued

A study subject will be discontinued from the study if the Investigator is unable to insert a punctal plug in to the study subject's lower punctum, they have experienced a complication (intra-operative exclusion criteria) during surgery, the punctal plug has been extruded after the surgical visit (Visit3), study subject has used a prohibited concomitant therapy, is non-compliant, has missed scheduled study visits, has personal reasons, has relocated out of the area or has a desired to withdraw from further participation in the study in the absence of a medical need as determined by the Investigator. Other reason – the study subject was discontinued for a reason other than those listed above, the Investigator must specify the reason

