5.5 Study Subject Withdrawal or Termination Criteria

Each study subject will be informed that they are free to withdraw from the study at any time. The Investigator, the Investigator in consultation with the Medical Monitor, or the Medical Monitor may exercise his or her medical judgment to terminate a study subject's participation in the study if it is in the best interest of the study subject. A terminated study subject will be followed through Day 14 or until the condition has resolved or has become medically stable.

Medical Monitoring for this study will be conducted by:

[name]
Phone (Office): [contact]
Phone (Cell): [contact]
Email: [contact]

The name of the Medical Monitor and contact information will be provided to each study site.

Mati Therapeutics Inc. reserves the right to terminate the study at any time. Every effort will be made to collect all data required by the protocol during or following the study subject's early termination visit.

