5.5.2.2 Handling of Discontinued Study Subject

A study subject may voluntarily discontinue (withdraw) from the study at any time they choose. Notification of discontinuation will be clearly documented on the appropriate Case Report Form. If a study subject elects to withdraw from the study during the study follow-up period, the Investigator will make every effort to have the study subject return to the clinic for an end of study safety evaluation and the removal of the masked punctal plug. A study subject who is discontinued from the study **will be replaced**.

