7.4.6 Early Exit Visit

Any study subject exiting the study early, the Investigator must remove the study subject's masked punctal plug. In addition, the Investigator should record the following:

- a. Investigator evaluation of ocular pain

NOTE: The Investigator that interviewed and record the subject's response to ocular pain at Visit 4 (Day 1 post-op) should interview the subject at this visit

- b. Monocular Distance Visual Acuity (Uncorrected and Best-Corrected)
- c. Manifest Refraction

- d. Inspection of the masked punctal plug via the slit lamp
- e. Slit-Lamp examination

NOTE: The Investigator that performed slit-lamp evaluation at Visit 4 (Day 1 post-op) should perform the slit-lamp evaluation at this visit.

- f. Fundus examination
- g. Removal of the masked punctal plug
- h. Recording of any reported adverse event(s).
- i. Concomitant medication

Any changes, discontinuation or addition of an open-label medication(s) must be recorded on the Concomitant Medication CRF.

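### Section 5.5.1.2 can be read as requiring discontinuation for non-compliance or missed visits; a site that applies it so loses obtainable Day 14 pain and cells/flare data, probably from few subjects

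*Combined protocol and SAP*

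**What the plan says.** Section 5.5.1.2 is one sentence stating that a subject is to be discontinued if any listed item applies. The items include "study subject has used a prohibited concomitant therapy, is non-compliant, has missed scheduled study visits, has personal reasons". It does not say how many visits must be missed or what counts as non-compliance. By contrast, Section 5.5.1.1 makes termination depend on the Investigator's medical judgement.

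Section 5.5.1 introduces these lists as exit-form reasons: "The primary reason for a study subject early exiting the study should be selected from the following standard categories". It also says that at a subject's last visit "they will have their masked punctal plug removed and a study exit case report form (CRF) must be completed".

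Section 5.5.2.2 provides for an end-of-study safety evaluation and plug removal. "A study subject who is discontinued from the study" is then replaced. Section 7.4.6 says: "Any study subject exiting the study early, the Investigator must remove" the plug. That Early Exit Visit also records pain and a slit-lamp examination.

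Follow-up to Day 14 is written for other groups. Section 5.5 says: "A terminated study subject will be followed through Day 14 or until the condition has resolved or has become medically stable". Section 7.7.1 (required NSAID, corticosteroid or immunosuppressant) and Section 7.9.1 (rescue) have similar wording.

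Pain at Days 1, 3, 7 and 14 is the primary endpoint (Section 4.2.1). Efficacy is analysed on observed data, with Last Observation Carried Forward only as an optional sensitivity analysis (Section 10.4.3).

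**The concern.** Leaving the study and missing a visit are different events. A subject who misses Day 3 and returns on Day 7 can still give a Day 14 score. If the list works as a trigger, that subject is scored, exited and replaced on Day 7, and the Day 14 score is never taken. A replacement restores the head count but not the outcome of the person who was randomised. Because the wording sets no threshold, two sites could also handle the same missed visit differently.

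**Working it through.** The plan gives no missed-visit rate, dropout rate or power (Section 10.5), so there is no figure of its own to reproduce.

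**1. Is any later assessment scheduled?** No. Sections 5.5.1, 5.5.2.2 and 7.4.6 provide plug removal, one exit examination and replacement. The general commitments set no visits. Section 5.5.1 says "all efforts will be made to complete and report the observations as thoroughly as possible". Section 5.5 says "Every effort will be made to collect all data required by the protocol during or following" the early termination visit, straight after reserving the sponsor's right to stop the study; Section 5.6 repeats this.

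**2. Which scores are lost?** Suppose the exit examination takes place at the next scheduled visit.

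| Missed | Exit at | Lost |
|---|---|---|
| Day 1 | Day 3 | Days 7, 14 |
| Day 3 | Day 7 | Day 14 |
| Day 7 | Day 14 | none |
| Days 1 and 3 | Day 7 | Day 14 |
| Days 3 and 7 | Day 14 | none |

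Day 14 is lost in every pattern that loses anything. If a site brings the exit examination forward, before the next scheduled visit, more is lost: a missed Day 3 then costs Days 7 and 14, and a missed Day 7 costs Day 14.

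**3. How many Day 14 scores?** Let m be the chance of missing any one visit, independent across visits. The values 3%, 5% and 10% are assumptions. The visit windows (±1, ±1 and ±2 days for Visits 5, 6 and 7) favour the low end. The base is 75 subjects, with exit at the next attended visit.

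*Two misses needed.* Only missing Visits 4 and 5 and attending Visit 6 ends participation before Day 14, with probability m²(1−m). The Day 14 score would otherwise have been given with probability m²(1−m)².

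*One miss suffices, Visit 4 attended.* Only missing Visit 5 and attending Visit 6 matters, with probability m(1−m). The Day 14 score would otherwise have been given with probability m(1−m)².

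| m | Two misses: exits of 75 | Two misses: scores lost of 75 | One miss: exits of 75 | One miss: scores lost of 75 | One miss: scores lost of 25 placebo |
|---|---|---|---|---|---|
| 3% | 0.07 | 0.06 | 2.18 | 2.12 | 0.71 |
| 5% | 0.18 | 0.17 | 3.56 | 3.38 | 1.13 |
| 10% | 0.68 | 0.61 | 6.75 | 6.08 | 2.03 |

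For example, at 10% with one miss: 0.10 × 0.90² = 0.081, and 0.081 × 75 = 6.08.

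The two readings have different bases. The two-miss case includes a missed Visit 4; the one-miss case leaves it out, and counting it would raise those figures. Exits for non-compliance cannot be sized because the term is undefined.

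**4. What would this do to power?** The pain-free rates below are those quoted in Section 2.1 for the 0.3% eye-drop trials. They are an illustration, not design assumptions. Power = Φ[(d − 1.96·SE₀)/SE₁], where SE₀ is the pooled and SE₁ the unpooled standard error, with 50 active and 25 placebo. For 86% against 46%, d = 0.40, SE₀ = 0.109 and SE₁ = 0.111, giving 95.3%. With 5% or 10% of Day 14 scores lost in each arm and not replaced, it is 94.3% or 93.2%. For 84% against 38%, the three values are 98.4%, 98.0% and 97.4%. The drop is about 0.4 to 2 points.

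**The case against.** The best counter-argument is that the list is a set of labels, not a rule. Section 5.5.1 calls the lists exit-form categories, and the sentence ends with a catch-all for other reasons. Personal reasons and relocation describe why someone left, not what the site must do. Sections 10.1 and 10.4.2 allow single visits to be excluded, which presupposes that a subject with a deviation can supply others. Section 7.9 treats some prohibited medication as a protocol deviation, although prohibited therapy is on the same list. Visits is plural, which favours the reading with under 1 of 75 lost.

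Much of this stands, and it is why the point is conditional. It does not remove the ambiguity. Two neighbouring items are mandatory exits elsewhere: a listed surgical complication (Section 5.3) and plug extrusion after surgery (Section 6.1.7.4). A site could fairly read the whole sentence in that way.

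The contrast with Day 14 follow-up elsewhere is also weaker than it looks. Those sentences read as clinical follow-up and set no schedule of pain or cells/flare scores.

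A reader might infer more than the documents support:

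- *That every missed visit ends participation.* The text is mixed, and nothing shows how sites would apply it.
- *That the result is biased or the sample shrinks.* No direction of bias is shown, and replacement is meant to restore the count.
- *That replacement harms the comparison through the arm assigned.* A replacement takes the next number in sequence (Section 10.6.1), but no harm follows from that alone.
- *That a subject with one missed visit would be dropped from the ITT set unless Section 10.1 changes.* Section 10.1 is permissive and concerns non-compliance that could significantly affect efficacy; a single missed visit does not clearly qualify. Section 10.6.3 also has subjects and visits assessed before the code is broken, although the interim analysis in Section 10.4.7 is unmasked.

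**Conclusion.** The concern holds in a limited form. Where a site treats non-compliance or missed visits as a trigger, the plan stops scheduled pain and cells/flare assessments in a subject who could still attend, and Day 14 is what is mainly lost.

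The size is unknown and probably small: under 1 of 75 Day 14 scores if two misses are needed, and about 2 to 6 of 75 on the less favourable one-miss reading with Visit 4 attended. Both rest on assumed, independent miss rates of 3% to 10% and on exit at the next attended visit. The illustrative effect on power is minor. The case for changing the text is that the loss is avoidable, could be applied unevenly across sites and cannot be recovered afterwards.

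The conflict over ITT is separate and does not depend on how Section 5.5.1.2 is read. Section 10.1 allows exclusions for major violations from the primary ITT population, while Section 10.4.2 keeps all data from every subject with a post-operative pain evaluation and leaves deviation exclusions to the per-protocol set.

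This is a should-fix item, held with medium confidence.

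**What to change.** - **Section 5.5.1.2:** state that a missed visit or non-compliance alone is recorded as a protocol deviation and does not end participation. Collect the remaining scheduled pain and slit-lamp assessments through Day 14, with or without the plug.
- **Plug:** leave earlier removal to the Investigator's safety judgement, and remove it in all cases by the final visit. The labels in Appendices 4 and 5 (Section 5.3 of each) warn of greater corneal risk with topical NSAID use beyond 14 days after surgery.
- **Section 5.5.2.2:** because these subjects remain in the study, do not replace them.
- **Section 10.1, separately:** align with Section 10.4.2, so that exclusions for non-compliance or other major violations apply only to the per-protocol set and the ITT analysis keeps all observed data.
- **Exit form:** a lost-to-follow-up reason would cover subjects who cannot be reached.

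The cost is a short amendment to three sections and one form entry. No visits are added, since Visits 6 and 7 are already scheduled. The downside is that some ITT data will come from subjects with reduced exposure.

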5.5.1.3 Reason for Disqualification

A study subject will be disqualified from the study if there was a failure to obtain written informed consent or HIPAA Authorization, improper entry (did not meet all inclusion/exclusion criteria), had a positive pregnancy test (after Visit 1).

5.5.2 Handling of Study Subject Termination, Discontinued or Disqualified

5.5.2.1 Handling of Terminated Study Subject

A terminated study subject will return to the clinic for an end of study safety evaluation and the removal of the masked punctal. A terminated study subject will receive appropriate treatment at the discretion of the Investigator. Notification of termination will be clearly documented on the appropriate Case Report Form. A terminated study subject is considered to have completed the study and **will NOT be replaced**.

5.5.2.2 Handling of Discontinued Study Subject

A study subject may voluntarily discontinue (withdraw) from the study at any time they choose. Notification of discontinuation will be clearly documented on the appropriate Case Report Form. If a study subject elects to withdraw from the study during the study follow-up period, the Investigator will make every effort to have the study subject return to the clinic for an end of study safety evaluation and the removal of the masked punctal plug. A study subject who is discontinued from the study **will be replaced**.

5.5.2.3 Handling of Disqualified Study Subject

Notification of disqualification will be clearly documented on the appropriate Case Report Form. If a study subject was inserted with a masked punctal plug, the Investigator will make every effort to have the study subject return to the clinic for an end of study safety evaluation and the removal of the masked punctal plug. A study subject disqualified from the study **will be replaced**.

5.6 Premature Termination or Suspension of Study or Study Site

Mati Therapeutics Inc. reserves the right to terminate or suspended the study at any time. Every effort will be made to collect all data required by the protocol during or following the study subject's early termination visit.

If representatives of Mati Therapeutics Inc., the Principal Investigator, the Study Monitor (Clinical Research Associate [CRA]), the Medical Monitor, or the FDA officials discover conditions arising during the study that indicate that the study will be halted or that participation by the study center will be terminated, this action may be taken after appropriate consultation with representatives of Mati Therapeutics Inc., the Principal Investigator, the CRA, and the Medical Monitor. Conditions that may warrant termination of the study include, but are not limited to the following:

- a. The discovery of an unexpected, serious, or unacceptable risk to a study subject enrolled in the study
- b. A decision on the part of Mati Therapeutics Inc. to suspend or discontinue testing, evaluation, or development of the product
- c. Failure of the Principal Investigator to enroll study subjects into the study at an acceptable rate
- d. Failure of the Principal Investigator to comply with pertinent FDA regulations and ICH Guidelines
- e. Submission of knowingly false information from the research facility to Mati Therapeutics Inc., or designee, the CRA, the Medical Monitor, or the FDA
- f. Insufficient adherence to protocol requirements.

Study termination and follow-up will be performed in compliance with the conditions set forth in 21 CFR 312.50 and 21 CFR 312.56.

6 STUDY AGENT

[figure not shown]
6.1 Study Treatments

6.1.1 Route of Administration

Each qualified study subject as they are enrolled in to the study will be sequentially assigned a Subject ID number. Treatment assignments for this study have been randomized (see [Section 10.6.1](#) for details on treatment randomization) to determine which one of the two masked punctal plug drug delivery systems a study subject will receive for the duration of the study.

[figure not shown]
6.1.2 Formulation, Appearance, Packaging and Labeling

The N-PPDS and p-PPDS consist of a drug insert that is placed in to the bore of an L-shaped punctum plug (Figure 1). The plug component for both the N-PPDS and p-PPDS products consists of an inactive medical grade silicone and 2% green colorant. The drug insert of the N-PPDS contains 204 µg of nepafenac (active ingredient) dispersed within a solid sustained release matrix. The drug insert for the p-PPDS consist of the same excipients as the N-PPDS however contains no active (nepafenac) ingredient (see [Appendix 6](#) for details).

Both the N-PPDS and the p-PPDS are provided pre-loaded on an insertion tool (see [Figure 2](#)).

Figure 2: Pre-Loaded masked study product on an Insertion Tool

The pre-loaded masked punctum delivery systems will be supplied in a sealed sterilized tray, labeled with investigational drug statement in accordance with applicable regulations.

6.1.3 Product Storage and Stability

All used and unused study punctum delivery system products must be stored in a secure area with controlled access. All plugs must be refrigerated between 36 – 46°F (2 – 8°C). All study punctum delivery system products have a retest date of 6 months.

A daily temperature log will be maintained documenting appropriate investigational product and required concomitant medication storage conditions and will be made available for the study monitor to inspect.

6.1.4 Starting Dose

One (1) to 2 days prior to their scheduled cataract surgery, a subject will be randomized (2:1) in to one of two treatment groups. The assigned punctal plug will be inserted in their lower punctum of their scheduled surgical eye.

NOTE: All systemic, topical and ophthalmic NSAIDs or corticosteroid medications, with the exception of a subject who has been prescribed and has been taking a baby aspirin (≤ 81 mg/daily), must be discontinued at least 48 hours prior to the insertion of the punctal plug.

6.1.5 Preparation for Insertion of Masked Punctal Plug

- a. A study subject will be placed in a recline position
- b. To anesthetize the area around the lower punctum, use a proparacaine or lidocaine soaked cotton-tipped swab, placing the swab directly on the lower punctum of the scheduled surgical eye for ~30 to 60 seconds (proparacaine or lidocaine can be irrigated into the canaliculus for better anesthesia if desired)
- c. The dilator is engaged vertically in the punctum with a gentle twisting motion. The dilator is moved to a horizontal position passing it into the proximal canaliculus dilating the punctum

- d. The punctum is dilated to **at least 1.0 mm**. Once the punctum is dilated to 1.0 mm, leave dilator in place for 15 to 30 seconds to allow the sphincter to fully relax

NOTE: For smaller puncta, hold and rotate the dilator in the punctum and canaliculus for a longer period of time (1 – 2 minutes or longer). Dilation may require very firm pressure. Add more anesthesia if needed.

6.1.6 Masked Punctal Plug Insertion

- a. While dilating, prep the plug to insert it in the punctum
- b. Remove dilator and immediately attempt to insert the plug before the sphincter starts to close

NOTE: The punctum may constrict before the plug can be inserted, additional dilation would then be required. If a plug is partially inserted (e.g., cap not flush with the lid) the plug should be removed and the punctum re-dilated or dilated to a larger diameter. Placement of the plug can then be re-attempted. Multiple attempts are sometimes necessary.

- c. After insertion the punctal opening should be visually inspected using a slit-lamp to confirm the retention and correct placement of the plug, with the cap still visible. The position of the study plug may be adjusted with forceps, if necessary.

NOTE: Any questions or concerns regarding the insertion or removal of a punctal plug contact:

[name]
Phone (Office): [contact]
Phone (Cell): [contact]
Email: [contact]

6.1.7 Unable to Insert/Extruded/Lost Masked Punctal Plug

6.1.7.1 Unable to insert masked punctal plug

If the plug cannot be inserted after a few attempts with gentle dilation, the subject will not be eligible for the study. Lubricants are not to be used.

6.1.7.2 Punctal Plug extruded pre-operative

If a study subject extrudes their plug prior to surgery, a new plug will be inserted in the lower punctum of the subject's scheduled surgical eye. The study subject will then be rescheduled for surgery in 1 to 2 days after re-insertion of the new plug. The punctal plug will remain in the study subject's lower punctum during cataract surgery and for a period of 2 weeks following surgery.

6.1.7.3 Punctal Plug extruded during surgery

If a study subject extrudes their plug during the surgical procedure, a new plug will be inserted in to the lower punctum of the subject's surgical eye upon completion of the surgery. The punctal plug will remain in the study subject's lower punctum for a period of 2 weeks following surgery.

6.1.7.4 Punctal Plug extruded after surgery

A study subject that has noticed a plug has been extruded or lost during the follow-up period after surgery should immediately contact the Investigator and/or his/her staff and return to the Investigator's office as soon as possible. The Investigator will discontinue the study subject from the study and place them on open-label post-op medication(s) deemed necessary for the patient's welfare by the Investigator.

For any study subject where the plug has been lost, the Investigator will retro-illuminate or palpate the canaliculi to confirm the plug has not migrated into the canal. Information regarding the loss of any plug must be recorded in the source documents, CRFs and Accountability Logs.

NOTE: If an extruded plug can be located by a study subject, the plug should be returned and collected by the Investigator and/or his/her staff. If the plug tears or has separated, report this as a technical complaint ([Section 8.6](#)). Retain the plug for accountability of investigational supplies.

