2.2 Rationale

Past clinical studies with topical dosing of 0.1% and 0.3% ophthalmic suspensions of Nepafenac (NEVANAC®/ILEVRO®) have demonstrated the safety and efficacy of Nepafenac in the treatment of pain and inflammation associated with ocular surgery. The objective for this study is to evaluate the use of a punctal plug drug delivery device that can deliver a sustained, safe and effective concentration of Nepafenac to a subject undergoing cataract surgery, for the treatment of post-operative ocular pain and inflammation.

Placebo has been selected as the control group. This will allow the results obtained from this study to be compared to treatment results from similarly design Phase 3 and 3B studies of Nepafenac.

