4.2 Study Endpoints

The study will be complete when 75 study subjects (75 eyes) have been evaluated at Visit 7 (Day 14 post-op) or have been terminated from the study.

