10.4.3 Analysis of the Secondary Endpoint(s)

The secondary efficacy variable will be the severity of ocular inflammation (anterior chamber cells and flare) report at visit 4, 5, 6 and 7 (post-op days 3, 7 and 14). For analyses using the intent-to-treat (ITT) data set, all data from all subjects with at least one post-operative follow-up inflammation evaluation will be included. For the per protocol (PP) analyses dataset, data from subjects or visits with significant protocol deviations will be excluded.

Efficacy analysis of primary and secondary endpoints will be based on observed data only. In the case of a significant amount of missing data, Last Observation Carried Forward may be used for sensitivity analysis.

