10.4.5 Adherence and Retention Analyses

N/A

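### Visits after post-operative plug loss go missing from the efficacy analyses and no plug-retention analysis is planned, so Day 7 and Day 14 results are largely conditional on keeping the plug

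*Combined protocol and SAP*

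**What the plan says.** All references are to the combined protocol and SAP.

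- **Purpose.** Section 2.2 sets out to evaluate a plug that can "deliver a sustained, safe and effective concentration of Nepafenac". Section 6.1.8 has it in place through surgery and for two weeks afterwards.
- **Loss after surgery.** Section 6.1.7.4: "The Investigator will discontinue the study subject from the study and place them on open-label post-op medication(s"). Section 5.5.1.2 lists among the reasons for discontinuation that "the punctal plug has been extruded after the surgical visit (Visit3").
- **Replacement.** Section 5.5.2.2: "A study subject who is discontinued from the study will be replaced".
- **Study completion.** Section 4.2: "The study will be complete when 75 study subjects (75 eyes) have been evaluated at Visit 7 (Day 14 post-op) or have been terminated". A discontinued subject is in neither group. Section 5.5 follows terminated subjects through Day 14; no such follow-up is stated for discontinued subjects.
- **Missing data.** Section 10.4.3: "Efficacy analysis of primary and secondary endpoints will be based on observed data only". Last observation carried forward is an optional sensitivity analysis if much is missing, with no threshold given.
- **Retention.** The whole entry under "10.4.5 Adherence and Retention Analyses" is N/A.
- **Limits on the effect.** Sections 10.4.2 and 10.4.3 keep in the ITT set all data from anyone with at least one post-operative evaluation. Section 7.4.6 asks for pain and slit-lamp grades at early exit. Sections 6.1.7.2 and 6.1.7.3 give a new plug to eyes that lose one before or during surgery.

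**The concern.** In a trial of a delivery device, losing the device is part of the result and not incidental dropout. Section 2.3.1 names plug loss as a known risk. Under the rules above, a subject who loses the plug contributes nothing after exit, a substitute is enrolled, and the study closes on subjects who reached Visit 7 or were terminated. The later the visit, the more its result is restricted to eyes that still had the plug.

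Two things are at stake. First, Section 2.2 chose placebo so that results could be set beside the Phase 3 nepafenac studies. The Day 14 table in Appendix 5 uses all randomized subjects as its denominator. An observed-data Day 14 rate here would not share that denominator, and if eyes that lost the plug would count as failures, the comparison would flatter the plug. Second, the rate and timing of plug loss by arm are what the next trial's design would need, and no analysis of them is specified.

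**Working it through.** **No figure to reproduce.** Section 10.5 states that no formal sample size was calculated, and no power, effect size or loss rate is given. What follows is illustration; the loss rates are assumptions.

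**Inputs**
- Allocation 50:25 (Section 4.1; 25 blocks of three in Section 10.6.1: 25 × 3 = 75).
- Two-sided 5% level (Section 10.4.1).
- Day 14 pain-free rates for 0.3% nepafenac drops against vehicle: 86% vs 46% and 84% vs 38% (Section 2.1, Appendix 5). These come from eye drops, and are used here as if they were the rates among eyes that keep the plug.
- Assumed post-operative loss by Day 14: 5%, 10% or 20%.

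**Step 1: equal loss, with loss counted as not pain-free.** Write pA and pP for the rates in retained eyes and lA and lP for the loss proportions. The difference in retained eyes is pA − pP. The difference over all eyes is pA(1 − lA) − pP(1 − lP).

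| Loss, both arms | 86 vs 46 becomes | Difference | 84 vs 38 becomes | Difference |
|---|---|---|---|---|
| 0% | 86.0 vs 46.0 | 40.0 | 84.0 vs 38.0 | 46.0 |
| 5% | 81.7 vs 43.7 | 38.0 | 79.8 vs 36.1 | 43.7 |
| 10% | 77.4 vs 41.4 | 36.0 | 75.6 vs 34.2 | 41.4 |
| 20% | 68.8 vs 36.8 | 32.0 | 67.2 vs 30.4 | 36.8 |

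**Step 2: unequal loss (86 vs 46).**
- 20% active, 5% placebo: 68.8 − 43.7 = 25.1 points.
- 5% active, 20% placebo: 81.7 − 36.8 = 44.9 points.

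The retained-eye analysis shows 40 points in both cases.

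**Step 3: loss related to symptoms.** Suppose 46% of eyes in each arm would be pain-free, so there is no effect. If 20% of active eyes and no placebo eyes lose the plug, and none of the lost eyes is pain-free, the retained active rate is 0.46 / 0.80 = 57.5%, a spurious benefit of 11.5 points. Exchanging the arms gives a spurious deficit of the same size. If lost eyes are pain-free as often as the rest, there is no bias.

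**Step 4: power of a loss-as-failure analysis.** Fisher's exact test, two-sided 5%, 50 and 25 subjects:

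| Loss, both arms | 86 vs 46 | 84 vs 38 |
|---|---|---|
| 0% | 93.3% | 97.3% |
| 5% | 88.4% | 95.2% |
| 10% | 83.4% | 92.5% |
| 20% | 72.8% | 85.0% |

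These figures leave out replacements. At 20% loss, reaching 75 retained eyes needs 75 / 0.80 = 93.75, so 94 enrolled. With about 62 and 31 analysed, power for 86 vs 46 is 84%, not 73%.

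**Step 5: is retention estimable?** Yes. The plug is inspected at Visits 2 to 7 (Table 1), and losses go on the CRF and accountability log with a suspected date (Sections 6.1.7.4 and 6.2). If 45 of 50 active plugs were retained, the exact (Clopper-Pearson) 95% interval would be 78.2% to 96.7%.

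**The case against.** A reader might infer that subjects who lose a plug are dropped from the analysis altogether, so that every reported success rate covers only eyes that kept it. The documents do not support that. Sections 10.4.2 and 10.4.3 retain everyone with at least one post-operative evaluation, with all their data. Early-exit grades are collected. Plug loss is not among the examples of a major violation in Section 10.1, and nothing removes a replaced subject from the ITT set. Day 1, one of the four primary time points, allows about a day for loss and is little affected. Only visits after exit are missing, together with any subject who loses the plug before a first post-operative evaluation. This objection stands.

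Four further points have weight.

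- **Retention data.** Section 10.4.1 promises frequency distributions for all categorical variables, so plug inspections may be tabulated anyway. Retention in Section 10.4.5 may also mean subject retention, as in Section 5.4. On either reading, no by-arm plug-retention estimate with an interval, and no time to loss, is specified.
- **Choice of question.** What the drug does while the plug is in place is a legitimate question for a pilot, and counting loss as failure scores some comfortable eyes as failures. This argues for a sensitivity analysis, not a new primary analysis, especially as the primary variable is pain severity.
- **Power.** The fall in Step 4 is a cost of the loss-as-failure analysis, not harm done by the present plan.
- **Same plug in both arms.** This makes similar loss plausible, but does not assure it.

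**Conclusion.** The concern holds for the later visits. Followed as written, the rules on discontinuation, replacement and observed data make Day 7 and Day 14 results largely conditional on keeping the plug, and no analysis of plug retention is specified. The claim that all efficacy results exclude eyes that lost the plug does not hold.

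The size depends on a loss rate that the documents do not give. With equal loss of 5% to 20% and 86% vs 46% in retained eyes, the gap between the retained-eye difference and the all-eyes difference is 2 to 8 points. Unequal or symptom-related loss could move the comparison in either direction, by 11.5 points in the extreme case of Step 3. With little loss, the matter is small; the plan should let the reader see which case applies.

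**What to change.** 1. **Section 10.4.5.** Replace N/A with the proportion of plugs retained at each of Visits 4 to 7 by arm, with exact 95% confidence intervals, and time to plug loss.
2. **Sections 10.4.2 and 10.4.3.** State that every randomized subject who loses a plug stays in the ITT set alongside any replacement, with all values up to and including early exit. Say to which visit an early-exit grade is assigned.
3. **Sensitivity analysis.** Pre-specify one that counts visits after plug loss as not successful, applied to the pain versus no-pain tabulation in Section 10.4.9 and to inflammation response. The latter needs complete and partial response (Section 4.2.2) to be defined first.

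Settle the wording before the interim analysis in Section 10.4.7, which unmasks data.

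The cost is SAP wording and one or two extra tables from data already collected. Success rates and power will be lower in the sensitivity analysis, as Steps 1 and 4 show; the main analysis keeps its observed-data basis. Clinical handling after plug loss is left as written.
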